Specific Aim 2: Conduct a pilot RCT comparing CBTi-CB (n=30) to SE (n=30) delivered remotely to (a) assess the acceptability and feasibility of RCT procedures; (b) determine the distribution and variability of the primary outcomes (insomnia severity, health-related functioning); and (c) assess potential mechanisms of change (sleep-related behaviors; sleep-related beliefs; sleep self-efficacy; and cannabis use motivation) within the CBTi-CB and SE conditions.

The proposed project addresses a key objective articulated in the most recent **NIDA Strategic Plan**, specifically, to “develop and test novel treatments based on the science of addiction” (Objective 3.1). This work is significant because of the large and growing number of US adults who use cannabis to manage their insomnia. Given the extent of daily cannabis use in users of cannabis for insomnia, intervening on sleep in this group represents the opportunity to engage and improve outcomes in those with heavy cannabis use. The study is innovative because it targets insomnia, a highly comorbid condition in a group of non-treatment seeking individuals, and proposes that improvement in sleep will reduce cannabis use and improve health-related functioning. The impact is enhanced by leveraging telemedicine approaches to optimize reach of the treatment.

RESEARCH DESIGN AND METHODS

Overview of approach. The purpose of this project is to adapt, iteratively refine, and pilot test an existing CBTi intervention for use in adults who currently use cannabis for insomnia (CBTi-CB). The proposed work is consistent with Stages IA/IB of the NIH Stage Model of Intervention Development.^{20,21} Also in line with these recommendations, the pilot trial will gather data on the extent to which participation in the CBTi-CB intervention is associated with changes in the proposed mechanisms of action of the intervention.^{20,21} The proposed project has two primary aims: (1) adapt and iteratively refine remotely-delivered CBTi-CB to address the unique needs of individuals using cannabis for insomnia and develop and refine a matched remotely-delivered Sleep Education Control (SE) condition; and (2) conduct a pilot randomized controlled trial (RCT) comparing remotely-delivered CBTi-CB to SE to (a) assess the feasibility of RCT procedures; (b) determine the distribution and variability of the primary outcomes (insomnia severity, health-related functioning); and (c) assess potential mechanisms of change.

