Consistent with Stage 1B research, the primary goals for the pilot RCT are to obtain information about the feasibility of the proposed RCT and estimate the distribution and variability of primary and potential mechanistic outcomes within intervention and control conditions. Initial analyses will involve calculating the attrition rates for 6- and 18-week follow-up assessments in each study group and identifying predictors of drop-out. We will also quantify session attendance and note the percent of participants who did not complete all sessions to identify ways to decrease drop-out and non-compliance to the intervention. Additionally, we will examine all participant feedback from the *Session Feedback Forms* and descriptive data from the measures of treatment integrity and therapist fidelity measures. To examine treatment integrity and fidelity (*the Session-Specific Adherence Rating Scales* and the *Therapist Skill/Competence scale*), inter-rater reliability will be examined with Yule’s Y statistic, by contrasting therapist results with those of the raters, as well as by contrasting those of the two independent raters. The items will be summed to produce overall competency summary scales. Cronbach’s alpha will be used to examine the internal consistency of each summary scale separately for the therapist and raters. The items and rating scales (anchors) will be further refined (added, eliminated or modified), if necessary, based on discussion of face validity and analysis of item appropriateness. These items will be used to monitor therapist skill and fidelity to the intervention protocol and to maintain the integrity of the intervention.

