The primary outcomes of interest include insomnia severity, functioning, and frequency of cannabis use. Potential mechanisms of the intervention include sleep-related behaviors (e.g., changes in time in bed, regularity of sleep schedules) and sleep-related cognitive factors (e.g., changes in sleep-related beliefs, self-efficacy to manage sleep without cannabis, motivation to use cannabis to manage sleep). Based on recent guidelines for Stage 1B research, we will calculate means and standard deviations for primary and mechanistic measures at baseline, post-treatment, and follow-up, as well as change scores for the CBTi-CB and SE groups. In line with recent recommendations for analysis of data from pilot studies, we will focus on estimation of confidence intervals for between-group differences at baseline and all follow-ups.

Moreover, although we recognize that the proposed project will not have adequate power to serve as a definitive study of intervention effects, to prepare for analyses for the future large-scale definitive trial we will compare the outcomes between the two study groups. We hypothesize that intervention participants will have less severe insomnia, better functioning, and lower frequency of cannabis use at follow-ups. The primary outcomes are hypothesized to meet the assumptions of continuous variables, and we will consequently use t-tests to make comparisons. If, however, the distribution of a measure is skewed, alternative modeling strategies (e.g., Poisson regression) will be used. We will examine separate models by sex (i.e., stratified analyses). We will also conduct exploratory analyses of how potential mediators (e.g., self-efficacy) relate to changes in insomnia and cannabis use, and will examine whether changes in insomnia and cannabis use are correlated. Although our sample size is not sufficient to conduct formal mediation analysis, results will inform the identification of those variables that best capture the mechanisms for intervention effects. We will use an intent-to-treat framework.

HUMAN SUBJECTS CONSIDERATIONS

For all phases of this study, approval will be obtained from the Institutional Review Board at the University of Michigan. This research is also covered by a Certificate of Confidentiality from NIDA.

Specific Aim 1-Phase 1: Qualitative Interviews

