Modified Marijuana Motives Questionnaire (MMQ)		X			
Medical Marijuana Use		X			
Prescription Misuse (BOYD)		X		X	X
Side Effect Checklist (SECL)		X		X	X
Marijuana withdrawal checklist revised (MWC-R)		X		X	X
PEG Three-item Scale Assessing Pain Intensity and Interference		X		X	X
BRFSS Model 16(Marijuana Use Type)		X		X	X
Multidimensional Fatigue Inventory (MFI-20)		X		X	X
Epworth Sleepiness Scale		X		X	X
Therapy Evaluation Questionnaire		X		X	
Working Alliance Inventory-SR				X	
Daily Sleep/Wake Diary		X	X	X	X
Actigraphy		X		X	X
Session Attendance			X	X	

Primary outcomes: The ultimate goal is to use this pilot study to provide all of the necessary elements to conduct a future fully-powered RCT comparing these two conditions. We hope to assess the acceptability and feasibility of RCT procedures to determine the distribution and variability of the primary outcomes (insomnia

severity). This will be measured by the change from baseline Insomnia Severity Index score to the score at study completion.

All remuneration for the study will be in the form of gift cards or cash. Participants will be remunerated with a \$40 for the completion of baseline assessment, \$40 for completion of each follow-up assessment, \$20 for completing four out of seven days of the daily online survey for every week before the first follow up and \$10 for completing four out of seven days of the daily online survey for the week before the 2nd follow up, plus an additional \$10 incentive for a urine drug screen at both follow ups. Participants will also receive \$30 to compensate them for any potential charges related to the use of their technology. Participants who do not complete all therapy sessions will still receive the \$30 to cover technology costs, however, they must have completed at least one phone session.

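### Intent-to-treat is stated, but with t-tests only and no rule for missing outcomes the default is an unadjusted available-case comparison

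*Combined protocol and SAP*

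**What the plan says.** The analysis is described in the Data Analysis text under Specific Aim 2 (Research Design and Methods). On the comparison of arms it says: "The primary outcomes are hypothesized to meet the assumptions of continuous variables, and we will consequently use t-tests to make comparisons". One alternative is offered, and its trigger is the shape of the distribution, not missing data: "If, however, the distribution of a measure is skewed, alternative modeling strategies (e.g., Poisson regression) will be used". The emphasis is on estimation: "we will focus on estimation of confidence intervals for between-group differences at baseline and all follow-ups". The section closes with "We will use an intent-to-treat framework".

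The Primary outcomes paragraph for the RCT (Human Subjects Considerations, Specific Aim 2) defines the insomnia measure: "This will be measured by the change from baseline Insomnia Severity Index score to the score at study completion". The RCT assessment table schedules the ISI at screening, about 8 weeks and about 16 weeks.

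The plan does expect losses. It will test for missingness, calculate attrition by arm, go on to "identifying predictors of drop-out", and report flow and retention by CONSORT. It does not say how any of this would enter the between-arm estimate. No imputation, likelihood-based model or sensitivity analysis for missing outcomes is named.

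**The concern.** Intent-to-treat has two parts: analysing people in the arm to which they were assigned, and accounting for everyone randomised. A t-test delivers the first. It cannot deliver the second once outcomes are missing, unless something fills them in, and nothing is named to do so.

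Two things are at stake. The first is bias, if those who leave one arm differ in outcome from those who leave the other. CBTi-CB includes sleep restriction and SE gives no individualised advice, so different reasons for leaving are plausible, though not established. The second is precision. A t-test on raw scores makes no use of baseline, and a t-test on change uses it only by subtraction. The pilot is meant to supply the elements for a full trial, and the between-arm estimate with its confidence interval is one of its products.

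**Working it through.** **Inputs from the documents.** "Conduct a pilot RCT comparing CBTi-CB (n=30) to SE (n=30) delivered remotely" gives 30 per arm. Follow-ups are at about 8 and 16 weeks. No SD, effect size, correlation, alpha or drop-out rate is given, so there is no stated figure to reproduce. Everything else below is an assumption.

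**1. Who contributes to the 16-week comparison under the named method**

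| ISI available | t-test at 16 weeks or on change to 16 weeks |
|---|---|
| Screening, 8 and 16 weeks | Yes |
| Screening and 8 weeks only | No; 8-week score unused here |
| Screening only | No |
| Sessions missed, 16-week score given | Yes, as assigned |

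**2. Precision.** The 95% half-width in SD units is t(0.975, 2n-2) × √(2/n). For 30, 27, 24 and 21 observed per arm (0%, 10%, 20% and 30% missing) it is 0.52, 0.55, 0.58 and 0.62. With SD 5 that is 2.6, 2.7, 2.9 and 3.1 ISI points.

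**3. Bias by hand.** Assume:
- true effect -3, SD 5
- in CBTi-CB, 30-40% of those worse than average at week 8 miss week 16, against 10% of the others
- in SE, 15% leave at random
- correlation of baseline with each follow-up (r_b) 0.3-0.5, and between follow-ups (r_f) 0.6-0.7

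The mean of each half of a normal distribution is ±√(2/π) = ±0.798 SD. The week-8 mean among those still observed in CBTi-CB therefore shifts by:
- 30% case: 0.798 × (0.7 - 0.9)/(0.7 + 0.9) = -0.100 SD
- 40% case: 0.798 × (0.6 - 0.9)/(0.6 + 0.9) = -0.160 SD

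Raw week-16 bias = 5 × r_f × shift:
- smallest: 5 × 0.6 × 0.100 = 0.30
- largest: 5 × 0.7 × 0.160 = 0.56

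Change-score bias = 5 × (r_f - r_b) × shift:
- smallest: 5 × (0.6 - 0.5) × 0.100 = 0.05
- largest: 5 × (0.7 - 0.3) × 0.160 = 0.32

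All of these favour CBTi-CB.

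**4. Simulation of the same setting, 30 per arm**

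| Estimator | Mean (truth -3) | SE |
|---|---|---|
| t-test, week-16 score | -3.3 to -3.6 | 1.4-1.5 |
| t-test, change score | -3.0 to -3.3 | 1.4-1.7 |
| Likelihood, baseline and week 8 | about -3.0 | 1.2-1.4 |

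A complete-case analysis of covariance on baseline alone has SE 1.25-1.39, against 1.23-1.34 for the likelihood estimate. Most of the gain in precision is therefore baseline adjustment, not recovery of missing data.

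**5. Other drop-out mechanisms.** A second simulation in SD units used correlations of 0.5 (baseline with week 8), 0.4 (baseline with week 16) and 0.6 (between follow-ups). Drop-out was either random or a logistic function of the week-8 score.
- Random, 20% per arm: bias about 0.
- Same dependence on week 8 in both arms, 20%: about 0.
- Dependence in CBTi-CB only, at 10%/10%, 20%/20% and 10%/30% (SE/CBTi-CB): -0.05, -0.11 and -0.15 SD on week-16 scores (0.25, 0.55 and 0.75 points at SD 5), and -0.01 to -0.03 SD on change.

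**6. Leavers who miss both follow-ups.** The likelihood estimate then has only baseline to work with. Its bias is roughly 5 × (r_f - r_b²) × shift:
- smallest: 5 × (0.6 - 0.25) × 0.100 = 0.17
- largest: 5 × (0.7 - 0.09) × 0.160 = 0.49

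The estimates are then about -3.2 to -3.5, so the model does not remove the bias here.

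**The case against.** The strongest reply is that this is a pilot whose goals are feasibility and variability, that the plan admits it lacks power for a definitive test, and that any bias is small beside a half-width of at least 0.52 SD. On the measure the plan defines as primary, the change score, the bias is at most about 0.3 points in the assumed setting. SE is matched to CBTi-CB on attention, session number, length and format, so arm-specific drop-out is an assumption. If leavers miss both follow-ups, the change-score t-test can even be closer to the truth than the mixed model. All of this stands, and it limits the size of the point. It does not supply the missing definition of the analysis set or the missing-data method.

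Three stronger readings are tempting and are not supported.
- A reader might infer that losses will go unreported. The plan commits to attrition by arm, predictors of drop-out, missingness checks and a CONSORT flow diagram.
- A reader might infer a treatment-completer analysis. Someone who skips sessions but gives follow-up data is still analysed as assigned, and someone missing only week 16 still counts at week 8.
- A reader might infer a rule excluding people with missing outcomes. None is stated. Available-case analysis is simply what the named test does when nothing else is specified.

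**Conclusion.** The point holds as a gap in specification. Intent-to-treat is asserted but not made operational for missing outcomes, and the only named method defaults to an unadjusted available-case comparison by assigned arm.

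In the main assumed setting (section 3 of the check) the resulting bias is about 0.0-0.3 ISI points on change scores and 0.3-0.6 on raw 16-week scores. It is near zero if drop-out is random or acts alike in both arms. The small change-score figure depends on the assumed correlations and should not be generalised. The documents do not show that the trial's estimate will be biased, because they give no drop-out rate or mechanism.

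A baseline-adjusted repeated-measures model lowers the standard error by roughly 5-20% in these settings, mostly through baseline adjustment. It removes the bias only when drop-out is explained by observed data such as the week-8 score.

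**What to change.** Amend the Data Analysis text as follows.

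- **Analysis set:** all randomised participants, by assigned arm, whatever their session attendance.
- **Main estimate for each continuous primary outcome:** a repeated-measures mixed model with baseline value, sex (the randomisation block), visit (8 and 16 weeks), arm and arm-by-visit, with unstructured covariance. Report the arm difference at each visit with a 95% CI. Multiple imputation using baseline, the 8-week score and the identified predictors of drop-out would be an acceptable alternative.
- **Sensitivity:** one delta-shift analysis, in which imputed outcomes for those lost are worsened by a range of ISI points fixed in advance. This is needed because participants with no follow-up add almost nothing to the mixed model.
- **t-tests:** keep as supplementary available-case results.
- **Visit times:** reconcile the 6- and 18-week assessments named in the attrition analysis with the 8- and 16-week visits elsewhere, since these decide when an outcome counts as missing.

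The cost is SAP wording and slightly more analysis work, with no new data.

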Develop participant process/feedback measures. Participant process/feedback measures will be developed. Participants will be asked for their feedback regarding their experiences in the using a semi-structured post-treatment interview. Participants will be asked to share their impressions of each session (e.g., focused on content, length, personal relevance) and of the overall cohesion across therapy sessions. Questions regarding the acceptability of all study activities will be asked in addition to suggested changes for the future trial. Relevant revisions will be made to the manuals and protocol based on this feedback, and a session feedback form will be created to assess the helpfulness and relevance of session topics.

Specific Aim 2: Conduct a pilot RCT comparing remotely -delivered CBTi-CB to remotely -delivered

SE. The second aim of the study is to conduct a pilot randomized trial of CBTi-CB vs. SE (N = 60). This approach is pragmatic and real-world in nature, as both conditions will be delivered remotely to individuals who report using cannabis for insomnia, yet suffer at least mild insomnia. Participants for the RCT phase will be recruited in various ways, including from two Michigan licensed cannabis provisioning centers (OM of Medicine and Bloom City Club), online at UMHealthResearch.org, in the community via flyers, on social media, and at community events. Participants will be randomized to CBTi-CB or SE and undergo self-reported assessments of sleep/insomnia, substance use, and functioning before and after treatment (~8 weeks) and at 16-week follow-up. As many subjects as possible will also undergo objective sleep assessment with actigraphy, if feasible. The ultimate goal is to use this pilot study to provide all of the necessary elements to conduct a future fully-powered RCT comparing these two conditions. To ensure the rigorous conduct of this study, we will utilize the CONSORT checklist and flow diagram to document participant accrual, flow and retention at all stages of the study.

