Once generated, documents that include the randomization sequence will be password protected to avoid inadvertent access by research staff involved in the enrollment process. The treatment condition assignments will be sealed in envelopes according to the allocation sequence by either the project coordinator or the study data manager prior to the beginning of study recruitment. The randomization process will be overseen by our study data manager and the project coordinator will be notified of assigned condition for specific participants at the completion of all baseline assessments (by opening sealed envelopes). Randomization should occur at the baseline enrollment appointment. Initiation of the study treatment condition (either CBTI-CB or SHE) should take place within one week of study enrollment and randomization in order to provide enough time for all sessions to be completed within the 6-8-week treatment window.

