Following randomization, the participants will be provided with an actigraph sleep monitoring watch if it is deemed safe by investigators and the University of Michigan Office of Research (UMOR). By “safe,” we mean that the risk of transmitting COVID-19 via the actigraphy watches or by going into the office to mail/pick up/configure watches is very low. This risk level is likely to change during the course of the study, and decisions will be made on a case by case basis at enrollment. Participants who are given the option to participate in actigraphy sleep data capture will have the option to decline and still participate in the full study. The actigraph (Actiwatch Spectrum Plus, Philips Respironics, Murrysville, PA) is a small waterproof device the size of wrist watch (48 mm x 37 mm x 15 mm weighing 31 grams) that is meant to be worn continuously on the non-dominant wrist. An accelerometer integrates movement frequency and intensity into a single measurement. In addition, a photodiode sensor continuously monitors incoming light and stores the data in lux levels. The actigraphs are set at a sampling rate of 30 seconds. Activity and light data are downloaded to computer and sleep/wake activity is estimated using Actiware® – Sleep software and following published guidelines. Data is accessed through the Actiware® – Sleep software and is identified by study participation ID. Participants will be asked to wear the actigraphy activity tracker for one-week (at least 7 consecutive days) post-enrollment, for at least one-week post-treatment (at approximately 8 weeks' post-enrollment), and at least one-week pre final follow up (at approximately 16 weeks' post-enrollment). Watches will be returned to the study team after the first 7 days of wear, returned to the participant after the last therapy session, collected by the study team at the follow up assessment, returned to the participant approximately 1 week before the final follow up assessment, and collected by the study team at that final assessment. To do so, we will ask participants to either 1. send the actigraphy activity tracker back in the mail using a prepaid envelope, 2. leave it in a drop box located at some of the recruitment sites, or 3. have study staff meet the participant at home or in the community to pick up or drop off the actigraphy activity tracker. Participants will be asked to wear the watch for at least 7 days post-treatment and again for at least 7 days pre- final follow up, and will return the watch at their in-person follow up or via mail after their electronic/mailed follow up is completed. Actigraphy activity trackers will come with informational brochures from the Philips Respironics company and pre-paid return envelopes for the participants to mail them back after both baseline and post-treatment assessment time points. Once the participant completes the survey, research staff will review the survey prior to the participant leaving the room to assess for risk status.

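### RCT actigraphy: nothing requires the watch clearance or the participant's answer to be settled before allocation is revealed, so the objective-sleep subset may be formed after randomisation

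*Combined protocol and SAP*

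**What the plan says.** All references are to the combined protocol and SAP.

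- **Status of actigraphy.** The Specific Aim 2 overview in Research Design and Methods expects partial coverage: "As many subjects as possible will also undergo objective sleep assessment with actigraphy, if feasible".
- **Allocation.** The RCT recruitment procedures place randomisation at the baseline enrolment appointment, after baseline data collection. At that point "the project coordinator will be notified of assigned condition for specific participants at the completion of all baseline assessments (by opening sealed envelopes"). The text does not say when the participant, or those judging watch safety, learn the arm.
- **Provision of the watch.** The next paragraph of the same section begins: "Following randomization, the participants will be provided with an actigraph sleep monitoring watch if it is deemed safe by investigators" and the university's research office.
- **Criterion and timing of that judgement.** Safety is defined by infection risk: "we mean that the risk of transmitting COVID-19 via the actigraphy watches or by going into the office", which has to be very low. The risk is expected to change during the study, and "decisions will be made on a case by case basis at enrollment".
- **Refusal.** "Participants who are given the option to participate in actigraphy sleep data capture will have the option to decline and still participate in the full" [trial].
- **Analysis.** The Data Analysis section states an intent-to-treat framework and between-group confidence intervals at baseline and all follow-ups. It gives no rule for a measure collected in only some participants.

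**The concern.** Randomisation makes two groups comparable when membership of the analysed set is fixed before allocation, or is at least unaffected by it. Here the protocol places provision of the watch after the envelope. It does not say that the safety clearance and the participant's answer are obtained and recorded before it. If a participant who knows the arm is more or less willing to wear a watch because of it, those with actigraphy in the two arms are selected differently, and their comparison is no longer protected by randomisation.

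Two results are exposed. The first is any between-arm contrast in actigraphy, the trial's only objective sleep measure. The planned confidence intervals cover mechanistic measures, and the examples given for sleep behaviour (time in bed, regularity of schedule) are ones that a watch could supply. The second is the uptake rate. Acceptability and feasibility of the RCT procedures are Aim 2(a), and uptake measured after allocation could mix willingness to wear the device with reaction to the assigned arm.

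**Working it through.** **1. Order of steps in the RCT.** Reading the recruitment procedures in sequence:

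1. Full-study consent, then baseline assessment.
2. Randomisation at that appointment; the project coordinator learns the arm from the envelope.
3. Watch provided, if cleared and accepted.

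The position of step 3 is explicit. The clearance decision is placed only at enrolment, which is the same appointment as step 2, so its order relative to the envelope is not stated. The participant's answer has no stated position. The concealment text protects what enrolling staff know in advance of allocation and says nothing about steps taken afterwards.

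**2. Comparison with the beta phase.** In Specific Aim 1 - Phase 2 the watch is given during the baseline assessment and the condition is assigned afterwards. The RCT reverses that order and adds case-by-case clearance and a right to decline. The beta assignment was not randomised (it depended on gender and enrolment date), so it is a precedent for the order of steps only.

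**3. How large a bias could be.** The documents give no actigraphy uptake, SD or effect size, so there is no figure to reproduce. Everything below is an assumption used for scale.

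Suppose willingness to wear the watch is a standard normal trait correlated r with the sleep outcome, there is no treatment effect, and a proportion p of an arm accepts. The mean outcome among acceptors is then shifted by r × φ(z_p)/p SD, where z_p is the cut-off exceeded with probability p. The factor φ(z_p)/p is:

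- p = 0.8: 0.350
- p = 0.7: 0.497
- p = 0.6: 0.644
- p = 0.5: 0.798

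The spurious difference between arms is the difference of the two shifts:

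| Assumed uptake | Difference | r = 0.2 | r = 0.5 |
|---|---|---|---|
| 80% v 50% | (0.798 − 0.350)r = 0.448r | 0.09 SD | 0.22 SD |
| 80% v 60% | (0.644 − 0.350)r = 0.294r | 0.06 SD | 0.15 SD |
| 70% v 60% | (0.644 − 0.497)r = 0.147r | 0.03 SD | 0.07 SD |
| Equal, same direction of selection | 0 | 0 | 0 |
| 60% v 60%, opposite directions | 2 × 0.644r = 1.288r | 0.26 SD | 0.64 SD |

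The last row is an extreme case. It is included because it shows that equal uptake rates alone are not evidence of no bias.

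**4. Set against sampling error.** The half-width of a 95% confidence interval for a difference in means, in SD units, is t × √(1/n₁ + 1/n₂):

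- 30 per arm (full uptake): 0.52
- 18 per arm (60%): 0.68
- 24 v 15 (80% and 50% of 30): 2.026 × √(1/24 + 1/15) = 2.026 × 0.329 = 0.67

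In the 80% v 50% case the bias of 0.09 to 0.22 SD is about 13% to 33% of the half-width (0.09/0.67 and 0.22/0.67).

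**The case against.** The strongest reply has four parts.

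- **The gatekeeping criterion is not about arm or sleep.** Clearance rests on COVID-19 transmission risk and belongs to investigators and the university research office. This stands. A reader might infer that staff freely choose who gets a watch in the light of the allocation; the documents do not support that. What remains is mainly the participant's refusal.
- **The order is unstated rather than wrong.** The clearance may already precede the envelope, and only the project coordinator is said to be told the arm. Full-study consent comes before baseline, and the consent form was not available for this review, so an earlier recorded choice about the watch cannot be excluded. This also stands, and it is why the conclusion is that the subset may be, not is, formed after randomisation. It does not remove the point: the protocol leaves the order open.
- **Little depends on actigraphy.** The RCT primary outcome is ISI change. The Data Analysis section does not name actigraphy as the source of time in bed or schedule regularity, and the diary could supply both. The feasibility analyses listed there do not include actigraphy uptake, and the trial disclaims adequate power for intervention effects. All correct, and it limits the seriousness. Actigraphy is nevertheless scheduled at baseline and both RCT follow-ups, and a contrast by arm is a natural use of it.
- **The possible bias is small beside the sampling error.** True of the unequal-uptake cases above. But a confidence interval does not reflect this kind of error, and a larger next trial that copied the procedure would keep the bias while its intervals narrowed.

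A reader might also extend the point to the sleep diary. The documents do not support that: daily surveys are described for participants generally, appear in the assessment schedule and are remunerated, with no case-by-case offer and no separate right to decline.

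**Conclusion.** The point holds for actigraphy only. The watch is provided after randomisation, participants may decline it, and no text fixes the clearance or the answer before allocation is revealed. The actigraphy subset may therefore be formed after randomisation, with refusal the more plausible arm-related route. The ISI comparison is untouched.

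The size is unknown. The 0.09 to 0.22 SD for 80% v 50% uptake rests wholly on an assumed uptake split, an assumed r of 0.2 to 0.5 and a normal selection model. The bias is zero if uptake and the way participants self-select are both unrelated to arm. The documents neither show that arm-related selection will happen nor prevent it. The change is worth making because it is nearly free, not because the primary result is at risk.

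**What to change.** In the RCT recruitment procedures and the Data Analysis section:

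1. Make the COVID-19 safety clearance and obtain the participant's accept/decline answer before the envelope is opened, and time-stamp both in REDCap. The watch itself may be delivered later.
2. Define the actigraphy set as participants cleared and accepting at that moment.
3. Keep anyone who later refuses or does not wear the watch in that set, with the data counted as missing.
4. Report uptake and wear by arm.
5. Label actigraphy contrasts as descriptive within that subset.

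Steps 1 and 2 make membership of the set independent of arm. They do not remove bias from later non-wear that differs between arms, which is why steps 3 to 5 are needed as well.

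The cost is a reordering of steps within one appointment and one added REDCap record, with no extra visit, device or staff.
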